6.5 Treatment compliance

Compliance will be assessed by the investigator and/or study personnel at visit 2 and end of study visit. Pill counts will be used to assess compliance with HD statin therapy. This information should be captured in the source document at each visit. Non-compliance is defined as $<80\%$.

6.6 Patient education

All subjects will be counseled and given instructions in regards to study treatments. Subject education will include study treatment action, side effects, benefits and risks, dosage and administration, food-drug/drug-drug interactions, pregnancy/lactation warning, and when to call investigator/physician. Subjects will be instructed to inform physicians and dentists of study treatment intake and to list all prescription medications, over-the-counter medications, or dietary supplements they are taking or plan to take so study personnel knows about other treatments that may affect adverse event risk.

Table 1
Schedule of Events

	V1	V2	V3	V4	V5/EOS
	Screening/ Initiate HD statin therapy	1 st dose of evolocumab 8 weeks post HD statin therapy \pm 5 days	24 \pm 4 hours post 1 st dose of evolocumab	2 st dose of evolocumab 4 weeks (\pm 3days) post 1 st dose	8 weeks (\pm 5days) post 1 st dose of evolocumab
Informed Consent	X				
Inclusion/Exclusion Criteria	X				
Height and Weight	X				
Vital Signs (HR, BP)	X	X	X	X	X
Medical History	X	X	X	X	X
Review Prior/Concomitant Medications	X	X	X	X	X
Safety Labs (CMP and CK)	X ¹	X			X
Urine Or Serum Pregnancy Test ²	X				X
Ankle/Brachial Index	X	X			X
Physical Exam	X ³	X ³			
Laboratory Measurements – Blood Sampling	X	X	X		X
Laboratory Measurements- Urine Sampling	X	X			X
Dispense Study Drug(s)	X	X		X	
Assign/Continue HD Statin Therapy	X	X	X	X	
Administer Evolocumab 420mg/Q4 wk x 2 doses		X		X	
Drug Accountability		X		X	X
Adverse Events	X	X	X	X	X

¹ CMP laboratory results within 3 months of Visit 1 are acceptable. If not available, a blood sample for CMP will be obtained and results reviewed prior to HD statin therapy initiation.

² Urine or blood specimen for pregnancy test will be collected on women of childbearing potential at screening visit and end of study.

³ May be conducted as a nursing assessment if a physical was performed as standard of care \leq 1 month prior to screening or at visit 2 if no AE/SAE's have occurred.

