- Subject has received drugs via a systemic route that have known major interactions with background statin therapy within 1 month before randomization or is likely to require such treatment during the study period (e.g. cyclosporine, clarithromycin, HIV protease inhibitors, gemfibrozil)
- Female subject who is unwilling to use at least 2 effective birth control methods for at least 1 month before screening and 15 weeks after the end of treatment with investigational products, unless the subject is sterilized or postmenopausal
- Subject is pregnant or breast feeding, or planning to become pregnant or to breastfeed during receipt of investigational products and within 15 weeks after the end of study treatment
- Known previous hypersensitivity reaction/s to the investigational products' active components and excipients
- Subjects treated with any anticoagulant
- Patients treated with Prasugrel or Ticagrelor
- Subject likely to not be available to complete all protocol-required study visits or procedures, to the best of the subject's and investigator's knowledge
- History or evidence of any other clinically significant disorder, condition, or disease other than those outlined above that, in the opinion of the investigator, may compromise the ability of the subject to give written informed consent, would pose a risk to subject safety or interfere with the study evaluation, procedures, or completion

** Acceptable methods of contraception (birth control) while taking part in this study are:*

- *Total Abstinence (no sexual intercourse), absence of menstrual periods in women for more than one year after menopause (change of life), sterilization surgery, including tubal ligation (tubes tied) or hysterectomy (removal of the uterus or womb) in women or a vasectomy in men.*
- *Oral contraceptives (birth control pills), intrauterine device (IUD), implantable or injectable contraceptives (Norplant or Depo-Provera), contraceptive patch, vaginal ring or use of condom with spermicide. These methods must be used exactly as directed.*

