2.2 Study methods

2.2.1 Blood sampling

Phlebotomy sites will be carefully chosen to minimize risk and platelet activation. After discarding the first 2-3mL of free flowing blood, the blood collection tubes will be filled to capacity and gently inverted 3 to 5 times to ensure complete mixing of the anticoagulant. Tubes containing 3.2% trisodium citrate (n=3) will be used for flow cytometry, light transmittance aggregometry and thrombelastography. Tube containing hirudin will be used for shear-induced platelet aggregation and tubes containing 3.2% trisodium citrate will be used for platelet activation marker analysis.

- **Platelet Aggregation**

Platelet aggregation will be assessed in platelet-rich plasma using a Chronolog Lumi-Aggregometer (model 490-4D) with the AggroLink software package after stimulation with 2 and 5µM ADP, 1.2 mM AA and 4ug/ml collagen.

- **Platelet Activation by Flow cytometry**

Expressions of p-selectin, CD36, LOX-1, basigin (CD147, receptor for glycoprotein VI), and oxLDL on platelets will be assessed by flow cytometry using respective antibodies.

- **Platelet-fibrin clot characteristics by TEG6S**

The TEG6s instrument is a microfluidic fully automated cartridge-based device.

- **Lipid profile and Soluble Biomarkers**

After collection, plasma samples will be frozen at -70°C until analysis by commercially available enzyme linked immunoassay kits and ACL TOP 300 coagulation analyzer. Lipid profile will be assessed by conventional laboratory method and soluble markers such as oxLDL, LOX-1 receptor, fibrinogen, hsCRP, p-selectin, Atherox in plasma by enzyme linked immunoassay.

- Safety Labs including Comprehensive Metabolic Panel (CMP) and Creatine Kinase (CK).

2.2.2 **Urine Sampling**

Ten (10) mL of a spot urine specimen will be collected at baseline, 8 weeks post high-dose statin therapy and 8 weeks post first dose of evolocumab.

- **Urine 11-dh-TxB2 and 8-iso-prostaglandin F2_α**

Urine 11-dh-TxB2 concentrations by AspirinWorks test kit, an enzyme linked immunoassay (ELISA).

Urinary 8-iso-PGF_{2α} analysis by 8-iso-Prostaglandin F2_α ELISA Kit (Cayman Chemical Co. #516351).

3 **STATISTICAL CONSIDERATIONS/DATA ANALYSIS**

3.1 **Primary and secondary endpoints**

Primary endpoint

Relative difference in maximal ADP-induced platelet aggregation between high-dose statin therapy and high-dose statin plus evolocumab therapy

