7.2 Visit 2: HD statin + evolocumab 420mg Q 4 weeks therapy

7.2.1.1 Subjects will return to clinic for lab measurements (see section 2.2, blood and urine sampling) after 8 weeks (\pm 5 days) of HD statin therapy. Lab measurements will be obtained prior to first dose administration of evolocumab therapy.

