7.5.1.2 Adverse events assessment

7.5.1.3 Safety laboratory tests

7.5.1.4 Health and medication review

7.5.1.5 Assessment of treatment compliance (HD statin therapy)

7.5.1.6 Urine or serum pregnancy test for women of childbearing potential

7.5.1.7 Subjects to continue original statin therapy

7.5.1.8 Measure ankle/brachial index

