8.6 Reporting of Pregnancies

The sponsor will report all pregnancies and pregnancies occurring in the partner of a patient participating in the study or potential infant exposure through lactation within 10 calendar days of sponsor's awareness to amgen.

Pregnant, lactating women, or women planning to become pregnant or to breastfeed during receipt of investigational products and within 15 weeks after the end of study treatment are excluded from participating in this trial. Women of child-bearing potential recruited into the study must have a negative urine or serum pregnancy test prior to initiation of HD statin therapy (screening visit) and will undergo urine or serum pregnancy testing at the end of study visit. Women of child-bearing potential must agree to use at least 2 forms of medically accepted method of contraception during the entire study duration. Male participants will be advised to use a medically accepted method of contraception during the study duration. If a female partner conceives and becomes pregnant while the male subject is participating in this study, the sponsor will be notified as per the procedures described above. No further doses of IP would be administered in these cases.

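### Pregnancy is tested only at screening and end of study, so both evolocumab doses are given on a test that is weeks old

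*Combined protocol and SAP*

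**What the plan says.** The exclusion criteria in section 2.1.1 rule out a woman to whom this applies: "Subject is pregnant or breast feeding, or planning to become pregnant or to breastfeed during receipt of investigational products". The restriction extends to 15 weeks after treatment ends.

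The testing schedule is the same wherever it appears:

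- Table 1 marks the pregnancy test at Visits 1 and 5 only, and footnote 2 reads "Urine or blood specimen for pregnancy test will be collected on women of childbearing potential at screening visit and end of study".
- Section 7.1 places a test at Visit 1, and section 7.5.1.6 lists "Urine or serum pregnancy test for women of childbearing potential" at the end-of-study visit.
- Section 8.6 says that women of childbearing potential "must have a negative urine or serum pregnancy test prior to initiation of HD statin therapy (screening visit"). For the closing test, the same section says that these women "will undergo urine or serum pregnancy testing at the end of study visit".

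The required negative result is therefore tied to the start of the statin, not of evolocumab. The task lists for the two dosing visits (7.2 and 7.4) contain no pregnancy test.

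Urine is nevertheless available at Visit 2. Under section 2.2.2 a "spot urine specimen will be collected at baseline, 8 weeks post high-dose statin therapy and 8 weeks post first dose of evolocumab". Section 7.2.1.1, which refers to both blood and urine sampling, adds: "Lab measurements will be obtained prior to first dose administration of evolocumab therapy".

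**The concern.** The investigational antibody is first given about eight weeks after the only pregnancy test that precedes it, and again about four weeks later. A pregnancy that began after screening and was not recognised would not be found by any scheduled test until both doses had been given. The end-of-study test can only reveal such an exposure after the event.

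The protocol already treats exposure in pregnancy as something to prevent. It also treats Visit 2 as a safety checkpoint: the metabolic panel, creatine kinase and physical examination are all repeated there. The pregnancy test is not. Women of childbearing potential can be enrolled, since the age criterion is over 18 with no upper limit and section 8.6 sets rules for them.

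What is at stake is avoidable fetal exposure to the study drug. The trial's statistical conclusions are not at stake.

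**Working it through.** The documents state no test age to reproduce, so the check is visit-window arithmetic. Day 0 is Visit 1, with the pregnancy test and the statin start assumed to fall on the same day.

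**Inputs**

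- Visit 2 and dose 1: 8 weeks ± 5 days after statin start (Table 1; 7.2.1.1), which is 56 ± 5 days.
- Visit 4 and dose 2, Table 1: 4 weeks ± 3 days after dose 1, which is 28 ± 3 days.
- Visit 4 and dose 2, section 7.4.1.1: 12 weeks ± 3 days of statin, which is 84 ± 3 days from day 0.
- Visit 5: 8 weeks ± 5 days after dose 1 (Table 1; 7.5.1.1), which is 56 ± 5 days.

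**Age of the last test under the current plan**

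- Dose 1: 56 − 5 = 51 to 56 + 5 = 61 days.
- Dose 2, Table 1: 51 + 25 = 76 to 61 + 31 = 92 days.
- Dose 2, 7.4.1.1: 84 − 3 = 81 to 84 + 3 = 87 days.

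**Wait from dose 2 to the next scheduled test**

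- Table 1 (both visits counted from dose 1): 51 − 31 = 20 to 61 − 25 = 36 days.
- 7.4.1.1: Visit 5 falls on day 51 + 51 = 102 to day 61 + 61 = 122. The wait is 102 − 87 = 15 to 122 − 81 = 41 days.

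**Test age with a Visit 2 pre-dose test added**

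| | Now | With a Visit 2 test |
|---|---|---|
| Dose 1 | 51–61 days | 0 days |
| Dose 2, Table 1 window | 76–92 days | 25–31 days |
| Dose 2, 7.4.1.1 window | 81–87 days | 81 − 61 = 20 to 87 − 51 = 36 days |

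For any one woman the gain at either dose equals her interval from Visit 1 to Visit 2, 51–61 days. If the statin starts later than Visit 1, for example while laboratory results are awaited, each day of delay adds a day to the current test ages.

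**Do the other safeguards fill the gap?**

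- Two-method contraception (2.1.1, 8.6) lowers the chance of pregnancy but detects nothing.
- The health review and eligibility re-confirmation (6.2, listed at Visit 2 through 7.2.1.7) can bring a known pregnancy to light. The inclusion/exclusion row of Table 1 is not marked at Visit 2, and re-confirmation is not stated to precede dosing.
- Section 8.6 says "No further doses of IP would be administered in these cases". That sentence follows the text on pregnancy in a male participant's partner, so whether it covers participants is unclear. In either case it acts only once a pregnancy is known.

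**The case against.** The strongest reply is that this is a consistent design choice, not an error. Every relevant section gives the same two tests, the first before any study treatment, and nothing in the documents requires a test before each drug or each dose. The day ranges measure test age, not risk: the documents give no pregnancy rate, no fetal risk figure and no expected number of women of childbearing potential. Several safeguards operate throughout. Two contraceptive methods are required from at least a month before screening. Counselling under 6.6 includes a pregnancy warning. Section 6.4 lets the investigator add safety assessments case by case, which would allow a test after a missed period. The remedy is also partial, because dose 2 would still rest on a test some weeks old.

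Most of this stands as a limit on how often the test would matter. The plan does not contradict itself, the risk is unquantified, and the safeguards are real. They do not answer the narrower point: each one lowers the risk, depends on discretion or acts on a pregnancy already suspected, and none schedules a test that would find an unrecognised one before evolocumab. That the remedy is partial is no reason to forgo it, since it makes the test at dose 1 current and takes 51–61 days off the test age at dose 2.

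**Conclusion.** The concern holds as an inexpensive patient-safety improvement to a coherent plan; it should be made, but it does not undermine the trial. As written, evolocumab is given on a pregnancy test 51–61 days old at dose 1 and at least 76 days old at dose 2, and the next scheduled test follows both doses.

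The ranges rest on the stated visit windows and on a statin start on the day of Visit 1; a later start makes the test older. The number of women affected is not estimable and may be small. No effect on the primary endpoint or sample size is shown. A very early pregnancy could still be missed by a Visit 2 test.

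**What to change.** Add a pregnancy test at Visit 2 for women of childbearing potential, in Table 1, footnote 2, section 7.2 and section 8.6. Run it on the urine already collected before dosing, and require a negative result before the first evolocumab dose.

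Supporting clarifications:

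- Mark the inclusion/exclusion row at Visit 2 in Table 1. State in 7.2 that the re-confirmation under 6.2 is completed before dosing and that evolocumab is withheld if the patient no longer qualifies.
- Say in 8.6 that the stop on further doses covers participants, and what happens to the study statin after a positive test.

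Optionally, add a test at Visit 4, which would bring the test age at dose 2 to 0 days. That needs a new sample, because Table 1 schedules neither blood nor urine at that visit.

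The cost of the main change is one inexpensive test per eligible woman, one mark in Table 1 and a few sentences, with a slightly longer Visit 2. A woman withheld at Visit 2 has no post-evolocumab value and counts against the dropout allowance of 60 − 50 = 10 patients.

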7 TIMING OF ASSESSMENTS

7.1 Visit 1: HD statin therapy

7.1.1.1 Subject demographic and baseline characteristics

Demographic data to be collected on all subjects include: date of birth, age, sex, race, ethnicity. Height, weight, blood pressure, heart rate, relevant medical history/current medical condition present before signing informed consent, diagnoses and not symptoms will be recorded. Lipid and other CV medications will be recorded in eCRFs.

- Obtain safety laboratory test results (comprehensive metabolic panel and CK) to check for renal and hepatic function prior to starting/continuing HD statin therapy. Urine or serum pregnancy test will be performed for women of childbearing potential only.
- Laboratory measurements (see 2.2, blood and urine sampling) will be obtained prior to initiation of study-HD statin therapy
- Perform complete physical examination or nursing assessment if applicable
- Measure ankle/brachial index
- HD statin therapy
Eligible subjects may start HD statin therapy once it is confirmed that they meet all inclusion criteria and none of the exclusion criteria. Enrolled subjects for this study can include subjects who are statin-naïve or already on statin. Statin-naïve subjects will be started on HD statin therapy. HD statin therapy allowed for the duration of the study includes (a) atorvastatin 40mg and 80mg and (b) rosuvastatin 20 to 40mg. Please see below for HD statin therapy guidelines:
 - If not on statin→start HD statin therapy (atorvastatin 40mg or rosuvastatin 20mg as according to investigator discretion)
 - If on atorvastatin 40 mg once a day→continue
 - If on lovastatin, pitavastatin, simvastatin, or pravastatin→change to atorvastatin 40 mg once a day
 - If on atorvastatin 80mg once a day→continue
 - If on rosuvastatin 20 to 40mg once a day→continue
 - If on rosuvastatin 10mg once a day→increase to 20mg once a day
- Provide patient education and medication instructions form for HD statin use
- Drug Accountability of statin therapy

7.2 Visit 2: HD statin + evolocumab 420mg Q 4 weeks therapy

7.2.1.1 Subjects will return to clinic for lab measurements (see section 2.2, blood and urine sampling) after 8 weeks (\pm 5 days) of HD statin therapy. Lab measurements will be obtained prior to first dose administration of evolocumab therapy.

7.2.1.2 Assessment of treatment compliance (i.e. HD statin therapy)

7.2.1.3 Perform complete physical examination

7.2.1.4 First dose administration of evolocumab 420mg

7.2.1.5 Provide patient information hand-out for study drug. Second dose of study drug-evolocumab will be 4 weeks after first dose. Subject will continue assigned HD statin therapy.

7.2.1.6 Safety laboratory test

7.2.1.7 Health and medication review

7.2.1.8 Adverse events assessment

7.2.1.9 Measure ankle/brachial index

7.2.1.10 Collect vital signs (HR, BP)

7.3 Visit 3: 24 hours post first dose of evolocumab

7.3.1.1 Subjects will return to clinic 24 \pm 4 hours post first dose of evolocumab for lab measurements (see section 2.2.1)

7.3.1.2 Adverse events assessment

7.3.1.3 Health and medication review

7.3.1.4 Collect vital signs (HR, BP)

7.4 Visit 4: HD statin + evolocumab 420mg continue Q 4 weeks therapy

7.4.1.1 Subjects will return to clinic after 12 weeks (\pm 3 days) of HD statin therapy.

7.4.1.2 Assessment of treatment compliance (i.e. HD statin therapy)

7.4.1.3 Second dose administration of evolocumab 420mg

7.4.1.4 Adverse events assessment

7.4.1.5 Health and medication review

7.4.1.6 Collect vital signs (HR, BP)

7.5 End of study visit

7.5.1.1 Subjects will return to clinic 8 weeks (\pm 5 days) post first dose of evolocumab for lab measurements (see section 2.2.1, blood and urine sampling).

7.5.1.2 Adverse events assessment

7.5.1.3 Safety laboratory tests

7.5.1.4 Health and medication review

7.5.1.5 Assessment of treatment compliance (HD statin therapy)

7.5.1.6 Urine or serum pregnancy test for women of childbearing potential

7.5.1.7 Subjects to continue original statin therapy

7.5.1.8 Measure ankle/brachial index

7.5.1.9 Collect vital signs (HR, BP)

8 ADVERSE EVENTS

8.1 Adverse Event (AE) Definitions

An AE is defined as any untoward medical occurrence in a patient or clinical investigation subject administered a pharmaceutical product which does not necessarily have to have a causal relationship with this treatment. An adverse event can be any unfavorable and unintended sign (e.g., including an abnormal laboratory finding), symptom, or disease temporally associated with the use of a drug, without any judgment about causality (i.e., whether or not it is considered to be drug-related). This includes any newly occurring event or previous condition that has increased in severity or frequency since the administration of the study treatment/intervention.

A suspected adverse reaction means any adverse event for which there is a reasonable possibility that the drug caused the adverse event. A suspected adverse reaction implies a

lesser degree of certainty about causality than adverse reaction, which means any adverse event caused by a drug.

An adverse reaction means any adverse event caused by a drug. Adverse reactions are a subset of all suspected adverse reactions for which there is reason to conclude that the drug caused the event. An adverse event or suspected adverse reaction is considered “unexpected” if it is not specifically mentioned as occurring with the particular drug under investigation. Information about common side effects already known about the study drug/s drug can be found in the study drug/s package inserts. This information will be included in the subject’s informed consent and should be discussed with the subject during the study as needed.

8.2 Serious Adverse Event (SAE) Definition

An SAE is defined as an event that:

- is fatal or life-threatening;
- results in persistent or significant disability/incapacity;
- constitutes a congenital anomaly/birth defect;
- requires inpatient hospitalization or prolongation of existing hospitalization, unless hospitalization is for:
 - routine treatment or monitoring of the studied indication, not associated with any deterioration in condition
 - elective or pre-planned treatment for a pre-existing condition that is unrelated to the indication under study and has not worsened since the start of study drug
 - treatment on an emergency outpatient basis for an event not fulfilling any of the definitions of a SAE given above and not resulting in hospital admission
 - social reasons and respite care in the absence of any deterioration in the subject’s general condition
- is medically significant, i.e., defined as an event that jeopardizes the subject or may require medical or surgical intervention to prevent one of the outcomes listed above

8.3 AE Grading Scale

The descriptions and grading scales found in NCI Common Terminology Criteria for Adverse Events (CTCAE) version 4.03 will be used for AE reporting. Each AE term is associated with a 5-point severity scale.

8.4 AE Reporting

All SAEs and AEs which are not serious but which lead to permanent discontinuation of study medication will be captured in the CRF. Non-serious AEs which do not lead to discontinuation of study medication will not be collected.

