6 VISIT SCHEDULE AND ASSESSMENTS

Informed consent will be obtained from subjects meeting the inclusion criteria and none of the exclusion criteria before the initiation of any study-specific procedures. The study comprises of 2 periods: (1) high-dose (HD) statin therapy and (2) HD statin + evolocumab therapy. Subjects will be on a HD statin therapy for 8 weeks followed by the initiation of evolocumab 420mg Q 4 weeks x 2 doses, in addition to HD statin therapy for another 8 weeks. Required assessments for each study visit are listed in Table 1. Subjects should be seen for all visits on the designated day or according to the allowed window period (see Table 1).

The study requires 5 clinic visits. Each clinic visit (except visit 4) includes laboratory measurements, safety assessment, and health and concomitant medication review. A complete physical exam and safety laboratory assessment are required for visits 1 and 2.

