6.4 Safety assessments

Safety assessments will consist of monitoring and recording of adverse events and serious adverse events (see section 8). The occurrence of adverse events should be sought by non-directive questioning of the subject at each visit during the study. AEs may also be detected when these are volunteered by the subject during or between visits or through physical examination, laboratory test, or other assessments. Medical conditions/diseases present before starting the study drug are considered AEs only if they worsen after starting the study drug. Abnormal laboratory values or test results constitute AEs only if they induce clinical signs or symptoms, are considered clinically significant, or require therapy. Abnormal values that constitute a SAE or lead to discontinuation of administration of study drug must be reported and recorded as an AE. Adverse event collection will commence after screening and initiation of the HD statin.

Additional assessments required to ensure safety of subjects should be administered as deemed necessary by the investigator on a case by case basis.

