8.5 Procedures for Recording and Reporting of Adverse Events

All AEs will be reported to the principal investigator. For both serious and non-serious AEs, the investigator has the primary responsibility for AE identification, documentation, grading, and assignment of attribution to the study treatment/intervention. The sponsor will consider the investigator's view when assessing the safety of the drug and determining whether to report expeditiously to the FDA, local institutional review board (IRB), and other regulatory agencies.

AEs, occurring from the start of study medication administration through the last day of study participation must be recorded on the AE CRF with the following information:

- The intensity grade (grade 1, 2, 3, 4, 5; see CTCAE v4.03 grading)
- The relationship to the study drug(s)
- Attribution: An assessment of the relationship between the AE and the medical intervention (i.e., study drug administration). After naming and grading the event, the clinical investigator must assign an attribution to the AE using the following attribution categories:
 - The duration (start and end dates or if continuing at final exam)
 - Occurrence (known risks for study drug/s, underlying illness or population)
 - Expected
 - Unexpected
 - Other contributing causes
 - Action taken with study drug
 - Any other actions in response to event
- Outcome
 - Death related to AE
 - Recovered/resolved with sequelae
 - Not recovered/resolved
 - Recovered/resolved without sequelae
 - Recovering/resolving
 - Intervention for AE continues
 - Unknown
- Whether it constitutes a serious adverse event (SAE)

For serious adverse events not previously documented in study drug/s Package Insert (new occurrence) and are thought to be related to the study drug/s, the investigator may urgently require further information from the investigator for Health Authority reporting. Amgen or designee may need to issue an IND Safety Letter (Investigator Notification) to inform all investigators involved in any study with the same drug that this SAE has been reported.

All suspected unexpected serious adverse reactions (SUSARs) related or possibly related to evolocumab and their follow-up reports must be reported to Amgen within 24 hours of submission to the regulatory agency, IRB or IEC. A copy of any safety report involving an Amgen drug (e.g. evolocumab) submitted to the regulatory agency, IRB or IEC, must be faxed to Amgen, within 24 hours of such submission.

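### Sections 8.4 and 8.5 set conflicting rules for recording non-serious adverse events that do not stop study drug, and nothing says which governs

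*Combined protocol and SAP*

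**What the plan says.** **Section 8.4** has two sentences. The first defines what is kept: "All SAEs and AEs which are not serious but which lead to permanent discontinuation of study medication will be captured in the CRF". The second defines what is not: "Non-serious AEs which do not lead to discontinuation of study medication will not be collected".

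**Section 8.5** opens with "All AEs will be reported to the principal investigator". It continues: "For both serious and non-serious AEs, the investigator has the primary responsibility for AE identification, documentation, grading, and assignment of attribution". On the form itself it says: "AEs, occurring from the start of study medication administration through the last day of study participation must be recorded on the AE CRF". The items to be entered include a grade from 1 to 5, relationship to study drug, duration, action taken, outcome and whether the event is serious.

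**Section 8.7** sends the action taken to treat an AE to the AE CRF, without restricting which AEs.

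**Section 6.4** says: "Safety assessments will consist of monitoring and recording of adverse events and serious adverse events", and that sentence then refers the reader to section 8. It also has patients asked about AEs, non-directively, at every visit. **Table 1** marks AEs at all five visits.

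**Section 6** says of the visits: "Each clinic visit (except visit 4) includes laboratory measurements, safety assessment, and health and concomitant medication review". Sections 7.4.1.4 and 7.4.1.5 and Table 1 nevertheless place an AE assessment and a medication review at Visit 4, when the second evolocumab dose is given.

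**The concern.** Sections 8.4 and 8.5 are adjacent, and both say what goes on the CRF. A non-serious event that does not stop drug is left out under one and required under the other, so staff cannot tell which to do.

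What is at stake is the tolerability record. Under 8.4 a muscle complaint on high-dose statin, or an injection-site reaction after evolocumab, would be asked about at the visit and then not collected. In a single-arm study the statin-only period is the only internal reference for tolerability of the combination, so losing these events in either period removes that description. If practice varies between staff or over time, the counts would be incomplete to an unknown degree. Events not written down at the time may not be recoverable later.

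**Working it through.** The plan gives no AE rate and no AE analysis, so there is no figure to reproduce. The check is a comparison of the rules, one class of event at a time.

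| Class of event | 8.4 | 8.5 |
|---|---|---|
| SAE | captured | recorded |
| Non-serious, drug stopped permanently | captured | recorded |
| Non-serious, drug interrupted temporarily | unclear | recorded |
| Non-serious, drug continued | not collected | recorded |

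1. **Rows 1 and 2 agree.** These events are captured under every section.
2. **Row 3 is unclear within 8.4.** Its first sentence requires permanent discontinuation. Its second excludes events that do not lead to discontinuation, without the word permanent. Whether a temporary stop counts is not stated.
3. **Row 4 is the direct conflict.** The instruction in 8.5 to use the AE CRF covers AEs from first study medication to the last day of participation, with no limit by seriousness or by effect on drug. It also makes the investigator responsible for documenting and grading non-serious events by name. 8.4 says events in this row are not collected at all.
4. **Precedence.** 8.5 does not refer back to 8.4, 8.4 does not carve out an exception to 8.5, and no other section ranks them.
5. **Supporting sections.** 8.7 points the same way as 8.5. The questioning in 6.4 shows that the information will be obtained. Table 1 shows that AEs are assessed at each visit; it does not say which go on the form.
6. **Extent.** The planned exposure is 60 patients over 8 + 8 = 16 weeks and five visits. The share of all AEs falling in rows 3 and 4 cannot be computed from the documents.
7. **Visit 4.** Read literally, section 6 leaves Visit 4 without safety assessment and medication review. 7.4.1.4, 7.4.1.5, Table 1 and the each-visit questioning in 6.4 say otherwise.

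**The case against.** The best defence is that 8.4 sets the scope of the CRF, while 8.5 sets the time window and the data items. The word all in 8.5 attaches to reporting to the principal investigator; the CRF sentence speaks only of AEs. The serious yes/no item does not settle the matter, because the subset in 8.4 holds both serious and non-serious events and would need that item anyway. 8.7 requires follow-up only of drug-related AEs that led to permanent discontinuation. 6.4 defers to section 8, and for laboratory abnormalities it makes AE recording mandatory at a threshold close to that of 8.4.

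Selective collection can also be a legitimate choice. This is a phase IV pharmacodynamic study with no safety objective and no clinical endpoints, and it refers to package inserts for known side effects.

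Part of this stands. 6.4 and Table 1 are not independent rules that every AE be entered, and the plan could lawfully choose the narrower rule. But the defence has to supply a limit that 8.5 does not contain. It also fits poorly with the duty in 8.5 to document and grade non-serious events, since 8.4 denies collection and not merely CRF entry. On Visit 4, section 6 may be loose summary wording, because that visit has no laboratory sampling; the text still needs aligning.

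A reader might infer more than the documents support:

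- **That no AE rate could be reported.** Rates of SAEs and of AEs causing permanent discontinuation remain reportable for both periods under 8.4.
- **That laboratory safety is lost.** The metabolic panel and creatine kinase are scheduled at Visits 1, 2 and 5 whatever 8.4 says, although Visit 1 may use an earlier metabolic panel.
- **That most AEs would go unrecorded.** This is plausible, but the documents give no rates.
- **That a zero-event bound measures the loss.** With 0 events in 60, the one-sided 95% upper limit is 1 − 0.05^(1/60) = 4.9%; with the 50 patients the sample size needs, 1 − 0.05^(1/50) = 5.8%. These show what complete recording would allow one to say about an event never seen. They do not size the contradiction.

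**Conclusion.** The contradiction between 8.4 and 8.5 is real and unresolved by any other section. It is confined to non-serious AEs that do not lead to permanent discontinuation. For events where drug continues, recording depends on which section is followed, and under 8.4 their rates cannot be reported for either period. For temporary interruptions 8.4 is itself unclear.

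The effect is on tolerability reporting only. The primary endpoint, its analysis and the sample size are untouched, and the reporting of suspected unexpected serious adverse reactions in 8.5 does not depend on the answer. This should be fixed, but it does not threaten the study's main conclusion. The verdict rests on the section texts alone, with no assumption about how often such events occur.

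**What to change.** Adopt one AE capture rule and word 6.4, 8.4, 8.5 and 8.7 to match it.

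- **Low-cost option:** remove the restriction in 8.4 and let 8.5 be the rule. Add to section 3 a descriptive tabulation of AEs, separately for the statin-only period and for the period from the first evolocumab dose to Visit 5. The questions are already asked at every visit and the form's items are already listed, so the cost is a short amendment and modest extra CRF entry.
- **If selective collection is intended:** limit 8.5 and 8.7 to match 8.4, say how temporary interruptions are classified, and state the limit wherever safety is reported. This saves data entry but gives up rates for the excluded events.

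In the same amendment, reconcile the Visit 4 exception in section 6 with 7.4.1.4, 7.4.1.5 and Table 1. If it was meant to cover laboratory measurements only, say so. This is a wording change with no added procedures.
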